C) This would be a randomized, double-blind, placebo controlled trial. 1/2 of the patients would receive intra-operative secretin, the other half would receive saline placebo. Both the surgeon and patient would be blinded to the randomization assignment. The advantage of giving secretin would be that it may allow for the identification of a leak intra-operatively and subsequently allow for repair if the leak was identified prior to abdominal wall closure. While the safety profile of the drug is excellent, receiving the medication could theoretically cause an increased intraductal pressure which may cause a leak when one was not already present.

D) Human subjects are needed to evaluate intra-operative, intravenous secretin in patients undergoing pancreatic duct resection.

4. Design, procedures, materials and methods:

Use a level of detail similar to what would be used when submitting an article for publication in a peer reviewed journal. Explain the study procedures, data collection, and analysis process. Please define terms and explain concepts which might be confusing to reviewers who are not expert in the area of the study. If a formal protocol for the study exists, page references to the protocol are acceptable.

This study design is a prospective, double-blind, randomized-controlled trial. We will enroll patients in our institution undergoing pancreatic resection to receive either 1) one dose weight-based Secretin to be given once the closure of the pancreatic resection margin is complete 2) saline placebo.

Consent and basic demographics will be garnered by the physician in an office visit once the surgery has been scheduled and consent for the surgery is being obtained. The consent will be validated by the treating surgeon in the pre-procedure area on the day of the surgery.

The patient will undergo the scheduled surgery. Once the pancreatic anastomosis has been deemed acceptable by the attending physician, but prior to abdominal closure, the patient will be randomized to receive either Secretin (0.2 mcg/kg) or saline placebo. The attending surgeon will be blinded to this assignment.

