- Possible:** Follows as reasonable temporal sequence from administration. May have been produced by the patient's clinical state or by environmental factors or other therapies administered.
- Probable:** Clear-cut temporal association with improvement or cessation of test drug or reduction in dose. Reappears upon re-challenge. Follows a known pattern or response to test drug.

The primary outcome of interest will be the presence of pancreatic leaks based on the amount of drain amylase on or after POD#3. Secondary outcomes will include: 1) technical interventions intraoperatively directed to leak closure or manipulation of the anastomosis following Secretin or placebo stimulation 2) length of stay as a surrogate to complication severity after pancreatic surgery.

Patient demographics, risk factors, operative technique, randomization assignment and outcome data will be recorded on standard case report forms – **See Case Report Forms in Appendix**. Data will be stored in an encrypted hard-drive by a single agent ([name]) who is the only researcher who has access to the randomization data.

5. Inclusion/Exclusion Criteria:

Please provide detailed description of inclusion and exclusion criteria. If a formal protocol for the study exists, page references to the protocol are acceptable.

Inclusion criteria:

1. Scheduled for pancreatic surgery requiring pancreatic resection at DHMC
2. Age greater than 18 years old
3. Ability to provide written informed consent

Exclusion criteria:

1. Inability to provide written informed consent
2. Current ongoing acute pancreatitis
3. Pregnant or nursing mothers
4. Any medical condition which in the judgment of the Investigator renders participation in this study medically inadvisable.
5. Participation in an investigational clinical study for a drug or medical device within 30 days prior to Visit 1.
6. [Any known allergy to methylene blue.](#)

6. Financial Considerations:

Disclosure of financial impact on the participant is critical to informed consent. Insurance cannot be billed for research-related services outside the standard of care or paid for by the funding agency for

the study. The department, the study or the participant may be responsible for payment for research-related services. Participants should know which tests, visits, or procedures will be billed to them or their insurance and which ones will be paid by the funding agency for the study or the department.

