CRF, and then building a multivariable logistic regression model using the categorical variable of drain amylase >3x the upper limit of normal. The data from the multivariate regression will be reported as Odds Ratios.

The secondary outcomes are both categorical and continuous variables and thus we will use the Fisher's Exact test as well as the two-tailed student's t-test. A multivariable analysis is not planned for evaluating the secondary variable.

Randomization will occur in a block format of 5 and will be generated by the primary investigators.

c) Justify the sample size, using the concepts of power, type I error, and effect size if applicable. If a formal protocol for the study exists, page references to the protocol are acceptable.

A clinically significant absolute decrease of 15% (20% to 5%) in the pancreatic duct leak rate. Based on these estimates and a two-tailed test comparing proportions using the statistical calculator (<http://homepage.stat.uiowa.edu/~rlenth/Power>), we project an estimated sample size of **176 participants (88 per arm)** to demonstrate an absolute 15% reduction in the leak rate with 80% power at a two-sided alpha level of 0.05.

8. Data and Safety Monitoring:

Describe plans for data and safety monitoring to ensure the safety of subjects and the quality of the data. As described in federal guidance "... a variety of types of monitoring may be anticipated depending on the nature, size, and complexity of the trial. In many cases, the principal investigator would be expected to perform the monitoring function." This plan should include monitoring to determine:

The progress of the trial, including periodic assessments of data quality and timeliness, participant recruitment, accrual and retention, participant risk versus benefit, and other factors that can affect study outcome. Monitoring should also consider factors external to the study when interpreting the data, such as scientific or therapeutic developments that may have an impact on the safety of the participants or the ethics of the study.

Note: This section does not request information related to sponsor study monitor visits. This section requires a description of an adequate data and safety monitoring plan.

Interim analysis will be performed once 50% (88) patients have been enrolled. If more than 66% of cases of duct leak are in a particular study group, a formal comparison between groups will be performed with the use of a two-sided stopping boundary of 0.005%.

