Synthetic secretin is FDA approved to diagnose exocrine pancreas dysfunction by the functional secretin stimulated pancreas function test and to facilitate pancreatic duct cannulation during ERCP. It is identical in amino acid sequence to native human secretin.

There has not been any reported adverse drug reaction to human secretin stimulation. Rarely, in over 1000 patients who have undergone Secretin-enhanced pancreatic function tests, there is transient vasodilatory effect resulting in flushing of the face and lips with stable vital signs. Therefore, the risks of administering intravenous secretin are modest as described in the package label.

In doses (800cu SQ bid x 7 days) given in clinical studies greater than those offered in the current study, there were no adverse events reported

Secretin is not known to increase the risk of acute pancreatitis episodes in patients with chronic pancreatitis not presently having an acute pancreatitis attack. No allergic reactions have been reported with secretin in commercial use although the administration of a test dose 0.2 mcg IV is still recommended. No significant hemodynamic effects have been observed following administration of secretin. Otherwise, the risks of administering secretin are modest as described in the package label.

The risk of confidentiality should be low given the case report form will be only available to [name] and will be kept in a locked cabinet. All data will be entered on a password-protected Microsoft Excel spreadsheet. Any statistical analysis will be done with patient study numbers and initials for identification of patient.

15. Risk/Benefit analysis:

Describe why the risks to subjects are reasonable in relation to the anticipated benefits to participants and in relation to the importance of the knowledge that may reasonably be expected to result from the study.

A potential risk reduction of up to 15% for pancreatic duct leaks outweighs the given theoretical risks of one time Secretin administration.

16. Research Setting

a) Is this a multi-center study?

Yes No

If yes: Are you the lead investigator? Yes No *If*

you are NOT the lead investigator:

Name of lead investigator:

Institution where the lead investigator is located:

b) List all sites where research will take place and the CPHS at Dartmouth College is the reviewing IRB (e.g. DHMC Alliance Hospitals, DHMC Clinics, WRJ VAMC):

Dartmouth-Hitchcock Medical Center

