The Principal Investigator (PI) is responsible for ensuring all participants have provided informed consent to participate in this study unless the consent process is waived or altered by the CPHS. The PI may authorize other appropriately trained individuals to obtain consent from participants.

Please file the consent form in the medical record of each research participant if study participation may affect other medical treatment.

Explain how informed consent to research participation will be obtained. Please describe the consent process, including information about:

- Who has been authorized by the PI to obtain consent

- *The time interval between providing information potential participants about a study and having the consent form signed*
- *Any precautions taken to minimize the possibility of coercion or undue influence*
- *Plans for responding to a potential participant or a legally authorized representative who does not speak English, such as the use of a translator or a translated consent form*
- *Any aids used to simplify scientific or technical information, like a diagram*
- *Plans to accommodate the probable literacy level of potential participants*

Informed consent will be obtained by primary investigator in the clinic at the time of consent for surgery. Consent will be re-evaluated on day of surgery. We will use a translator for non English speakers and since the study is very simple, we will not use any aids. Literacy levels can be accommodated by having the consenting nurse or physician able to read the consent to the trial participants if necessary.

*I intend to obtain consent for research participation but I am requesting a waiver for the use of a signed and dated consent form. Please respond to the criteria listed in **Attachment I** and include an information sheet based on the CPHS template.*

*I am requesting an alteration of the consent process to exclude certain information that is ordinarily required. A list of the essential elements of consent to research participation is available on the CPHS website: <http://www.dartmouth.edu/~cphs/tosubmit/ConsentElements.html>. Please respond to **Attachment H**.*

*I am requesting a waiver of the entire consent process and use of a consent form. Please respond to **Attachment H**.*

Explain why any alteration or waiver to the consent process or form is necessary.

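### The primary investigators generate the randomization list and take consent, no text says how the next assignment is hidden or released, and a block of 5 cannot be 1:1

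*Combined protocol and SAP*

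**What the plan says.** All references are to the combined protocol and SAP.

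- **List generation, Section 7(b):** "Randomization will occur in a block format of 5 and will be generated by the primary investigators".
- **Consent, Section 26(a):** "Informed consent will be obtained by primary investigator in the clinic at the time of consent for surgery".
- **Time of randomization, Section 4:** "Once the pancreatic anastomosis has been deemed acceptable by the attending physician, but prior to abdominal closure, the patient will be randomized".
- **Blinding, Section 4:** "The attending surgeon will be blinded to this assignment". Section 3(C) says that surgeon and patient are both blinded.
- **Access, Section 4:** the data sit on an encrypted drive with one individual, "who is the only researcher who has access to the randomization data". Section 27(c) likewise says that one investigator keeps the data and no other investigator has access. The name is removed in this text.
- **Disclosure, Section 4:** a patient's assignment is revealed at discharge from the initial admission.
- **Patients who drop out before treatment:** exclusion criterion 4 in Section 5 rests on investigator judgment. Under Section 4, a patient given neither secretin nor placebo is not followed.
- **Planned split:** the Abstract and Section 7(c) plan 176 participants, 88 per arm.

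**The concern.** Concealing the next assignment keeps the decision to enrol and treat a patient independent of the arm that the patient would get. It is a separate safeguard from blinding, which protects care and assessment after allocation. Here the one sentence on randomization gives the list to the same role that takes consent, and no sentence describes a means of concealment. If a person who can influence whether a patient proceeds knows or can infer the next slot, the arms may differ in leak risk for reasons other than secretin. No analysis can reliably undo that afterwards.

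The same sentence sets a block size that cannot give the equal split on which the sample size is based.

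**Working it through.** **1. The plan's own figure.** Section 7(c): 20% against 5%, two-sided alpha 0.05, power 80%. With mean proportion 0.125:

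n = [1.960·√(2·0.125·0.875) + 0.842·√(0.20·0.80 + 0.05·0.95)]² / 0.15² = 75.1, so 76 per arm.

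With continuity correction: (75.1/4)·[1 + √(1 + 4/(75.1·0.15))]² = 87.95, so 88 per arm and 176 in total. The stated figure is reproduced, and it assumes equal arms.

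**2. Who can see the next slot.**

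- Section 7(b) has investigators, in the plural, produce the list. Whoever produces a list has normally seen it.
- Sections 4 and 27(c) allow one person access to the stored data. This limits who opens the file. It does not say how the next assignment is hidden at enrolment, or who passes it to the operating room.
- Envelopes, a central or web system, coded vials and a pharmacy-held list are all unmentioned.
- The blinding statements cover the surgeon and the patient. They do not cover others who consent or screen.

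**3. Where selection could still act.** The slot is used in theatre, so knowing the list in clinic is not the same as knowing that patient's arm. Near the day of surgery the order of cases is clearer. Until then a patient can be excluded on investigator judgment, and consent is re-evaluated that day (Section 26(a)). A patient withdrawn before theatre never enters the randomized set, and one not given study drug is not followed.

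**4. Inference from disclosed assignments.** Section 13(b) implies 120 × 0.8 = 96 participants a year, one per 365/96 = 3.8 days. Length of stay is not given, but drain amylase is checked to day 5. The most recent one or more assignments would therefore usually still be unknown when the next patient comes. The table gives the share of correct best guesses by someone who knows the block scheme and all earlier assignments except the last few (exact enumeration; chance is 50%).

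| Block scheme | Last 0 unknown | Last 1 | Last 2 | Last 3 |
|---|---|---|---|---|
| 5, randomly 3:2 or 2:3 | 62% | 58% | 54% | 52% |
| 5, always 3:2 | 72% | 64% | 62% | 60% |
| 4 | 71% | 58% | 54% | 50% |

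Disclosure at discharge with a published fixed block size therefore gives a modest advantage over chance. The table does not apply to someone who has seen the list, who need not guess.

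**5. Balance.** 176/5 = 35.2, that is 35 blocks plus 1 patient.

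- *Always 3:2:* 35 blocks give 105:70 before the last patient. This contradicts the planned halves.
- *Randomly 3:2 or 2:3:* arm size = 70 + Bin(35, ½) + Bernoulli(½) = 70 + Bin(36, ½). P(88) = C(36,18)/2³⁶ = 0.132, and P(82 to 94) = 0.971.
- *5 per arm (blocks of 10):* 17 blocks plus 6 patients. P(equal) = C(5,3)²/C(10,6) = 100/210 = 0.476, and the gap is at most 4.

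Exact two-sided Fisher power for 20% against 5% is 83.8% at 88:88, and 84.8% or 85.4% at 82:94, depending on which arm is larger.

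**The case against.** The best reply is that the plan does restrict access. One individual alone holds the randomization data on an encrypted drive, and only the removal of names prevents us from seeing whether that person is separate from enrolment. Consent comes well before randomization, the slot is used in theatre, and a blinded surgeon judges the anastomosis. No text identifies a person who both knows the coming slot and can stop a patient from proceeding. Section 30(a) also has an item on the investigational pharmacy managing study drugs. The tick is not readable, but no alternative plan follows.

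Much of this stands, and it limits the point. It does not supply a concealment mechanism, and it leaves sole access at odds with list generation by several investigators. A pharmacy role in drug management would not by itself be custody of the list.

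A reader might infer more than the documents support:

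- *That the person taking consent sees the list, or that selection occurred.* Nothing shows either.
- *That the consent texts contradict each other.* Section 4 refers to a physician, which is compatible with the primary investigator. The phrase "having the consenting nurse or physician able to read the consent to the trial participants if necessary" concerns literacy and at most hints at delegation.
- *That the bias can be given a size.* This needs the number of patients passed over and their leak risks, which the plan does not give.
- *That even blocks never reduce guessing, or always do.* Blocks of 4 are no less guessable overall than blocks of 5 that are randomly 3:2 or 2:3. Against a fixed 3:2 split they are less guessable. The plan does not say which is meant.

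**Conclusion.** The point holds as a design gap that should be fixed. The plan assigns list generation to the role that takes consent, describes no concealment or release of the next assignment, and discloses past assignments during enrolment. The weight rests on a basic safeguard that is undescribed and cheap to add, not on a bias figure. Any bias is unquantified and is probably limited by the timing and blinding in Section 4. Whether the single data holder also enrols patients cannot be seen in this text.

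The block rule is a smaller, certain defect. As written it cannot be 1:1 within a block and does not deliver 88:88 reliably: 13.2% of lists under randomly split blocks of 5, 47.6% if 5 per arm was meant. Under the random split the effect on power is negligible, so this is a matter of a correct and reproducible specification and does not make the trial underpowered.

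**What to change.** Replace the Section 7(b) sentence with:

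*Randomization will be 1:1 in permuted blocks of even size, not disclosed to study staff. The list will be generated and held by a party independent of consent, surgery and outcome assessment, and each assignment will be released only at randomization in the operating room.*

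Then:

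- Reconcile Sections 4, 7(b) and 27(c) on who generates, holds and sees the list. If a concealment procedure already exists, write it down.
- Amend the Section 4 sentence on disclosure at discharge, so that routine disclosure does not reach those who consent, operate or assess outcomes while enrolment continues.
- If 5 per arm was intended, say so.

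Blocks of 4 divide 176 exactly (44 blocks) and give 88:88 as randomized. Mixing 4 and 6 makes block ends harder to identify and keeps the gap to at most 2, with equal arms in about 78% of simulated lists. The main protection comes from independent generation and withheld assignments, not from the choice of block size.

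The cost is a few protocol sentences and a small list-preparation task for an existing independent party. The investigational pharmacy is one candidate if its role is confirmed. The sample size stays at 176.

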Funding Source (Sponsor): ChiRhoClin, Inc, and ChiRhoClin Research Institute. This is an investigator-initiated project. ChiRhoClin, Inc. will supply the drug, Secretin. [name] will also receive a small grant from the ChiRhoClin Research Institute to support the research coordinator's salary.

1. Abstract.

Provide an abstract of the proposed research in language that can be understood by a non-scientist. The abstract should summarize the objectives of this project and the procedures to be used, with an emphasis on what will happen to the subjects. (Maximum 250 words)

Pancreatic ~~anastomotic~~-leaks complicate pancreatic resection in approximately 20% of cases. The pancreatic anastomosis or repair has been referred to as the Achilles heel of pancreatic surgery. Unfortunately, despite recognition of this problem and multiple operative techniques proposed to prevent this complication, leaks continue to represent a major cause of morbidity for patients undergoing pancreatic surgery. Treatment of leaks often requires nutritional support with total parenteral nutrition to diminish the leak in addition to invasive interventions to contain the leak with drains, stents or in severe cases, reoperation. Experiential data suggest that intra-operative infusions of secretin, a naturally occurring hormone that stimulates bicarbonate release from the pancreas, following resection but just prior to abdomen closure, may identify a leak if present. If secretin can demonstrate evidence of leaking intra-operatively, the pancreatic duct leak may be able to be fixed prior to abdominal closure. We aim to determine if giving an intra-operative infusion of secretin will allow for identification and treatment of leaks after pancreatic reconstruction and prior to abdominal closure, leading to a reduction in the rate of pancreatic ~~anastomotic~~-leaks requiring intervention. We will perform a double-blind, randomized pilot study of 176 patients undergoing pancreatic resection (pancreaticoduodenectomy and distal pancreatectomy) at Dartmouth-Hitchcock Medical Center. 88 of those patients will receive an intraoperative secretin infusion prior to abdominal closure and 88 will receive a saline placebo. Our primary outcome of interest will be the rate of pancreas duct leaks in each group as measured by the amount of amylase present in the surgical drains on or after post operative day (POD)# 3 following surgery.

2. Objectives & Hypotheses:

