a) *List tests, visits, and procedures performed for only research purposes. These services are outside the standard of care. They would not be performed if the individual were not a research participant, and may not be billed to a health insurance plan.*

Note: 6a information must also be in "How is this different . . ." section of the consent form.

The administration of Secretin or placebo is for research purposes only and will not be billed to the patient. Drain placement, drain amylase measurement and the two week follow-up visit are per standard of care and will be billed directly to the patient.

b) *List the tests, visits, and procedures that may be standard care, but for which the funding agency for the study is paying.*

None

c) *Will the funding agency for the study be responsible for the above costs? Yes No
If No, describe who will be responsible (i.e., department or participant).*

Secretin will be supplied by ChiRhoClin, Inc and saline placebo will be supplied by the Section of Gastroenterology and Hepatology out of research funds maintained by the primary investigators. No additional tests, visits, or procedures will be performed for research purposes only.

PLEASE ENCLOSE THE DHMC BILLING GRID/PLAN. Also enclose the schedule of events or table listing all procedures from the sponsor protocol.

7. Statistical Methods and Review Statement:

a) *Specify the primary endpoint, as well as other endpoint(s).*

Primary Objective:

1. Pancreatic leak as defined by the ISGPF definition of post-operative pancreatic leaks

Secondary Objective:

1. Assess whether intervention is performed intra-operatively on the pancreatic anastomosis following Secretin or placebo injection.
2. Assess degree to which leakage severity, as a complication, increases length of stay.

b) *State the statistical analysis plan, including all hypothesis tests (e.g., t-test, chi-square), and estimation methods related to the primary endpoint. If a formal protocol for the study exists, page references to the protocol are acceptable.*

For the analysis of the primary endpoint, a categorical variable, we will use a two-tailed Fisher's Exact test to determine a p-value. We will then be able to calculate an absolute and relative risk reduction. We will also evaluate this variable using a student's t-test for means of amylase levels in the drain fluid. We will plan on performing univariate analysis of all of the potentially contributing variables outlined in the

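### Blocks of 5 cannot close evenly between two arms, so the randomisation rule as written conflicts with, and does not guarantee, the stated 1:1 allocation of 88 per arm

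*Combined protocol and SAP*

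**What the plan says.** The allocation rule is a single sentence at the end of section 7b: "Randomization will occur in a block format of 5 and will be generated by the primary investigators". No ratio within the block is given. No section mentions varying block sizes, unequal allocation, or a scheme that alternates the larger arm.

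Three other places describe equal arms:

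- Section 1 (Abstract): "88 of those patients will receive an intraoperative secretin infusion prior to abdominal closure and 88 will receive a saline placebo".
- Section 3, part C: "1/2 of the patients would receive intra-operative secretin, the other half would receive saline placebo".
- Section 7c, the sample size: "176 participants (88 per arm").

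The interim look also bears on this. Section 8 says "Interim analysis will be performed once 50% (88) patients have been enrolled". It opens a formal comparison if one study group holds more than 66% of the duct-leak cases.

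**The concern.** Blocking is meant to bring the arms level at the end of every block. With two arms and five places that never happens. Whoever prepares the list must add a rule that the protocol does not contain, and different additions give different trials.

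Two things are at stake. The first is that the allocation may depart from the stated ratio and arm sizes. The second is the interim trigger. It looks at the share of leak cases in a group, not at the leak rate, so a larger arm collects more cases even when the treatment does nothing.

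**Working it through.** **Inputs.** Block size 5 (7b). Total 176, 88 per arm (7c). Leak rates: "A clinically significant absolute decrease of 15% (20% to 5%) in the pancreatic duct leak rate". Design target: "with 80% power at a two-sided alpha level of 0.05". Primary test: "we will use a two-tailed Fisher's Exact test to determine a p-value". Interim look at 88 patients, with the trigger at more than 66% of cases in one group (section 8).

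**1. Reproduce the sample size.** With p1 = 0.20, p2 = 0.05 and mean 0.125:

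- Uncorrected: n = [1.96·√(2·0.125·0.875) + 0.8416·√(0.20·0.80 + 0.05·0.95)]² / 0.15² = 75.1, so 76 per arm.
- With continuity correction: n' = (75.1/4)·[1 + √(1 + 4/(75.1·0.15))]² = 87.9, so 88 per arm and 176 in total.

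The plan's figure is reproduced at 1:1, so the sample size is sound.

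**2. Fit of the blocks.** 176 = 35 × 5 + 1 and 88 = 17 × 5 + 3. Both the interim look and the end of recruitment fall inside a block, and every completed block is 3:2 or 2:3.

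**3. What each possible completion of the rule gives at 176.**

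- *Majority arm drawn at random per block.* The final difference is a sum of 36 independent values of +1 or −1 (35 blocks plus the last patient). Its SD is √36 = 6, so the SD of one arm's total is 3. P(88:88) = C(36,18)/2³⁶ = 0.132. P(each arm within 6 of 88, i.e. no worse than 94:82) = 0.97.
- *Strict alternation of 3:2 and 2:3.* One arm gets 18·3 + 17·2 = 88 and the other 87 after 175 patients, so 88:88 is reachable at patient 176.
- *Fixed 3:2.* 35·3 = 105 and 35·2 = 70, so 106:70 or 105:71 at 176.

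For comparison, simple randomisation of 176 gives a difference with SD √176 = 13.3.

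**4. Power.** Exact enumeration of the two-sided Fisher test at 0.05, for 20% v 5%:

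| Placebo : secretin | Power |
|---|---|
| 88 : 88 | 0.838 |
| 94 : 82 | 0.848 |
| 82 : 94 | 0.854 |
| 106 : 70 | 0.829 |
| 70 : 106 | 0.842 |

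All exceed the planned 80%.

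**5. Interim trigger.** Assume a 20% leak rate in both arms, so there is no treatment effect. Let X and Y be independent binomial counts with the arm sizes shown, and sum the probability that X/(X+Y) or Y/(X+Y) exceeds 0.66:

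| Arms at 88 patients | P(trigger) | of which larger arm |
|---|---|---|
| 44 : 44 | 0.15 | (equal arms) |
| 48 : 40 | 0.19 | 0.15 |
| 53 : 35 | 0.32 | 0.31 |

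The 53:35 row is what a fixed 3:2 list gives: 17 blocks make 51:34, and three more patients typically split 2:1. Under the random-majority list, the difference at 88 patients has an SD of about 4.3. Averaging the trigger probability over that distribution gives about 0.16. The distortion is therefore large only under a fixed 3:2 list.

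**The case against.** A reader might infer that blocks of 5 make 1:1 allocation impossible. That goes too far. Mixed 3:2 and 2:3 blocks with a random majority arm give each patient an even chance of either treatment, and strict alternation can reach 88:88. What stands is that neither scheme is written down.

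A reader might also infer that the trial will end near 106:70, with many more patients than planned in one arm. The documents do not support this. No section mentions a 3:2 ratio, and the Abstract and section 3 contradict it. Someone who read the whole protocol would be unlikely to build such a list.

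It can fairly be added that unequal arms neither bias the comparison nor invalidate Fisher's test. Randomly mixed blocks of 5 still balance better than simple randomisation (SD 6 against 13.3), and an exact tie has no inferential value in itself. Section 7c presents 176 as an estimate, and section 4 does not follow patients who receive no study drug, so exact analysed arm sizes were never assured. All of this stands, and it limits the severity.

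It does not remove the conflict. The protocol states a specific block size that cannot balance in a two-arm trial described three times as equal. Reading the sentence as five patients per arm does not rescue it, because the block size would then be 10 and the text would still need correcting.

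**Conclusion.** The concern holds as a conflict between the allocation rule and the stated 1:1 ratio. It should be fixed, but it is not critical. As written, the rule does not guarantee equal arms. On the most natural completion, a random majority arm, the ratio holds on average with a final difference of SD 6 patients. Power stays between 0.83 and 0.85 for every split examined, so a claim of material power loss would be wrong.

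The practical consequences are an undefined list and an interim trigger that loses neutrality as the arms diverge. The trigger result assumes 20% leak in both arms. It moves from 0.15 to about 0.16 on average with random-majority blocks, and to 0.32 only under the fixed 3:2 list that other sections contradict. It describes only how often a formal comparison is opened; the section 8 stopping boundary still applies afterwards. Who generates or sees the list is a separate question that this point does not decide.

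**What to change.** Replace the block-size wording in section 7b with an explicit rule, for example: *Participants are allocated 1:1 in permuted blocks of even size, 4 and 6 in random order, with block sizes not disclosed to surgeons or to staff who obtain consent.*

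This does not guarantee an exact tie. In simulation about 77% of lists are tied at 88 patients and about 77% at 176. The arms differ by at most 2 patients at those two points and by at most 3 at any point. If exact equality at both is wanted, fixed blocks of 4 (22 and 44 blocks) or 8 (11 and 22 blocks) give 44:44 and 88:88, at the price of a more predictable sequence. If five per arm was meant, state a block size of 10. Since 10 divides neither 88 nor 176, exact ties would then occur with probability C(8,4)·C(2,1)/C(10,5) = 0.56 at the interim look and C(6,3)·C(4,2)/C(10,5) = 0.48 at the end.

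The cost is one protocol sentence and a regenerated list for patients not yet randomised. The total stays at 176, and no extra patients or staff are needed.
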